3.3. Analysis populations

- Intention to treat population
All patients enrolled in the study
- Per protocol population
Patients receiving all three injections

4. Statistical Principle

The sample has not been powered to detect significant differences before and after treatments. Data will be analysed by simple descriptive statistics.

All patients enrolled will be followed up and included unless they withdrew from the study before the administration of the first dose. An intention to treat analysis will be carried out. Per protocol analyses may also be carried out alongside the intention to treat analysis if necessary.

Adherence to the intervention will be assessed by missed dose (protocol violation) and delayed / missed followup visits (protocol deviation).

4.1. Protocol violations

Patients will be allowed 28 days +/- 3 days between treatments. Where a dosing visit is > 3 days late it should be documented as a protocol violation.

Where the interval between 2 doses is > 42 days, the dose will be considered to have been missed. If a treatment is missed the subject will continue in follow-up but an additional subject will be recruited, so that a total of 8 subjects will receive all 3 doses.

Where the interval between two doses is between 32 to 42 days, this would be documented as protocol violations.

4.2. Protocol deviations

Patients will be allowed to attend for follow up visit 4 (week 9) +/- 1 day of schedule, visit 5 (week 14), +/- 1 week of visit schedule and visit 6 (week 20) must be a minimum of 85 days post final dose/+2 weeks. Any visits outside of this guidance will be considered a protocol deviation.

All protocol violations and deviations as well as number of patients involved will be enumerated at the end of the study. A patient will be defined as being compliant with the protocol if s/he has taken all the three injections on target (within window) dates. Adherence to intervention will be enumerated according to treatment/followup on target (within window), protocol violations/deviations and missed dose/followup across the study schedule as set out in dummy table (ii) in Appendix 1.

Data from all enrolled patient will be included in analysis of safety as specified in section 5.1.1. and 5.3. Metabolic and immunological outcomes of patients who have missed or delayed dose/followup will also be explored with analysis specified in section 5.1.2

5. Analysis strategy

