**Table 1: Schedule of study visits**

Visit number	Screening		Pre V1	Treatment							Follow up				Optional	
	-2	-1		1	1b	1C	2	3	3b	3C	4	Pre V5	5	6	7	any time post dosing
Weeks	These visits can be combined. Treatment must start within 3 months of screening commencing 		A minimum of 72 hours prior to visit 1	0	1 day post visit1	3 to 5 days post visit 1	4	8	1 day post visit3	3 to 5 days post visit 3	9	A minimum of 72 hours prior to visit 5	14	20	52	
Days				0			28	56			63 (or one week post final injection)		98	140 (85 days post final dose)	366 (311 days post. final dose +/- 14 days)	
Informed consent	X															
Study drug administration				X			X	X								
Follow up telephone call 24 hours post IMP				X			X	X								
Physical Exam & ECG	X			X			X	X					X		X	
 Serum for AABs and immune markers				X							X		X		X	
DRB1*0401 genotype	X															
MMTT				X									X		X	
Photographs at injection site				X			X	X			X		X	X	X	
Blood sample to accompany skin studies (optional)								X								
Stitch removal from biopsy site (optional)										X						
urine or random serum c-peptide post meal		X		X									X		X	
72 hour continuous glucose monitoring			Attach CGM	X								Attach CGM	X		X	
Serum for Cystatin C				X							X		X	X	X	
Urinalysis for blood, protein, and beta-2 microglobulin		X		X			X				X		X	X	X	
Serum and urine (morning) sample to measure gold concentrations				X pre dose	X 				X 		X		X	X	X	
T cell (immune biomarker) assays (blood)				X				-			X		X		X	
 LN aspiration 0/3-5d				X		X		X		X						
 Safety blood samples		X		X			X				X		X	X	X	
HbA1c measurement		X		X			X				X		X		X	
Vital signs	X	X		X			X	X			X		X	X	X	
Adverse Event assessment/con meds		X	X	X	X	X	X	X	X	X	X	X	X	X	X	
Urine pregnancy test		X		X			X	X					X	X		
Record of insulin use	X			X			X	X					X		X	
 Blood glucose profile/insulin usage				X			X	X					X	X	X	

Assessment of glycaemic control/review blood sugar recordings				X				X	X					X		X	
Skin biopsy (optional) 																	X
Contact hypersensitivity testing (optional) 																	X
Suction blister (optional) 																	X
XHFS survey				X										X			
ADDQoL				X										X		X	
DTSQs				X										X		X	
DTSQc														X			

Screening can be up to 3 months

Treatment visits 1, 2 and 3 should be every 28 days +/- 3 days and follow up visit 5 should be at 14 weeks +/- 1 week

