### **5.4 Subject compliance**

Patients will be allowed 28 days +/- 3 days between treatments, but every effort should be made to dose every 28 days. Where a visit is > 3 days late it should be documented as a protocol violation and scheduled as soon as possible, with subsequent dosing visits recommenced on a 28 day schedule after this. Where the interval between 2 doses is > 42 days, the dose will be considered to have been missed and the subsequent dose should be given. Subject attendance and compliance will be recorded. If a treatment is missed the subject will continue in follow-up but an additional subject will be recruited, so that a total of 8 subjects will receive all 3 doses.

Patients will be allowed to attend for follow up visit 4 (week 9 or one week post final injection) +/- 1 day of schedule, visit 5 (week 14), +/- 1 week of visit schedule and visit 6 (week 20) must be a minimum of 85 days post final dose/+2 weeks. There will also be an optional visit 7 (week 52) at a minimum of 311 days post final dose +/- 2 weeks. There will be an optional skin blister, an optional skin biopsy and an optional contact hypersensitivity testing performed anytime post-dose (referring to post final dose). Any visits outside of this guidance will be considered a protocol deviation.

**Figure 2** Chart indicating dosing schedule

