## 5.7 Concomitant health issues

Study drug should not be administered if a subject has had a febrile illness within the last 3 days as this may activate T cells non-specifically. Under these circumstances, the missed study visit should be delayed to the earliest next feasible date (but no longer than 14 days) and the study continued.

Females will be advised not to become pregnant within 85 days following the date of their final treatment of IMP and will be advised to continue using adequate contraception until this time point See section 6.2

Males will be advised not to father a child within 85 days following the date of their final treatment of IMP.

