2.3. Timing of final analysis

Final statistical analysis should commence after the Statistical Analysis Plan (SAP) has been finalised and the study data locked. Prior to database lock, the SAP must be finalised and signed off by CI and Trial Statistician. All outcomes will be analysed collectively at the end of the trial and completed within the timeframe agreed by the study team.

Table 1: Schedule of study visits

| Visit number | Screening | | Pre V1 | Treatment | | | | | | Follow up | | | | |
|---|---|----|--|-----------|-------------------|--------------------------|----|----|-------------------|--------------------------|----|--------------------------------------|----|-------------------------------|
| | -2 | -1 | | 1 | 1b | 1C | 2 | 3 | 3b | 3C | 4 | Pre V5 | 5 | 6 |
| Weeks | These visits can be combined. | | A minimum of 72 hours prior to visit 1 | 0 | 1 day post visit1 | 3 to 5 days post visit 1 | 4 | 8 | 1 day post visit3 | 3 to 5 days post visit 3 | 9 | A | 14 | 20 |
| Days | Treatment must start within 3 months of screening commencing. | | | 0 | | | 28 | 56 | | | 63 | minimum of 72 hours prior to visit 5 | 98 | 140 (85 days post final dose) |
| Informed consent | X | | | | | | | | | | | | | |
| Study drug administration | | | | X | | | X | X | | | | | | |
| Follow up telephone call 24 hours post IMP | | | | X | | | X | X | | | | | X | |
| Physical Exam & ECG | X | | | X | | | X | X | | | | | X | |
| *Serum for AAbs and immune markers | | | | X | | | | X | | | | | X | |
| DRB1*0401 genotype | X | | | | | | | | | | | | | |
| MMTT | | | | X | | | | | | | | | X | |
| Urine c-peptide post meal | | X | | X | | | | | | | | | X | |
| 72 hour continuous glucose monitoring | | | Attach CGM | X | | | | | | | | Attach CGM | X | |
| Serum for Cystatin C | | | | X | | | | | | | X | | X | X |
| Urinalysis for blood, protein, and beta-2 microglobulin | | X | | X | | | X | | | | X | | X | X |
| Serum and urine (morning) sample to measure gold concentrations | | | | X | X* | | | | X* | | X | X | X | X |
| T cell (immune biomarker) assays (blood) | | | | X | | | | X | | | X | | X | |
| *LN aspiration 0/3-5d | | | | X | | X | X | | | X | | | | |
| *safety blood samples | | X | | X | | | X | | | | X | | X | X |
| HbA1c measurement | | X | | X | | | X | | | | X | | X | |
| Vital signs | X | X | | X | | | X | X | | | X | | X | X |
| Adverse Event assessment/con meds | | X | X | X | X | X | X | X | X | X | X | X | X | X |

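### SAP 4.2 drops the protocol's second timing option for visit 4, so some visits that the protocol permits would be reported as protocol deviations.

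*SAP*

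**What the plan says.** **SAP.** Section 4.2 states "Patients will be allowed to attend for follow up visit 4 (week 9) +/- 1 day of schedule", and then "Any visits outside of this guidance will be considered a protocol deviation". The days row of SAP Table 1 runs "63 | minimum of 72 hours prior to visit 5 | 98 | 140 (85 days post final dose", so visit 4 is at day 63 with no alternative. The same section says that deviations, and the patients who had them, will be counted. Dummy table (ii) in Appendix 1 reports this visit by visit.

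**Protocol.** Section 5.4 gives "visit 4 (week 9 or one week post final injection) +/- 1 day of schedule, visit 5 (week 14), +/- 1 week". Protocol Table 1 gives the day of visit 4 as "63 (or one week post final injection". The protocol thus has two acceptable anchors for visit 4, and the SAP has one.

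**Dose timing.** Protocol 5.4 says "Patients will be allowed 28 days +/- 3 days between treatments", and SAP 4.1 uses the same interval rule. After a late dose the schedule continues "with subsequent dosing visits recommenced on a 28 day schedule after this". If a subject has had a recent febrile illness, protocol 5.7 says that "the missed study visit should be delayed to the earliest next feasible date (but no longer than 14 days) and the study continued".

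**The concern.** The SAP's deviation rule is narrower than the protocol rule it is meant to score. A site that follows the protocol and books visit 4 one week after the last injection can be recorded as deviating from that same protocol. The only reason would be that small permitted shifts in doses 2 and 3 have moved the date away from day 63.

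Two outputs could be affected. The first is the visit 4 column of dummy table (ii). With 8 patients, each wrong entry is 1/8 = 12.5% of that column. The second is the undertaking in SAP 4.2 to explore metabolic and immunological outcomes in patients whose dose or follow-up was missed or late. A patient correctly seen a week after a slightly late but in-window dose 3 could be placed in that group because of the SAP's date rule alone.

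**Working it through.** The documents give no figure on this point to reproduce, so the check is a direct enumeration.

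**Inputs**
- Interval between doses: 28 +/- 3, so 25 to 31 days (protocol 5.4, SAP 4.1).
- SAP visit 4 window: 63 +/- 1, so days 62 to 64 (SAP 4.2, SAP Table 1).
- Protocol one-week option: dose 3 + 7 +/- 1, so dose 3 + 6 to dose 3 + 8 (protocol 5.4).

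**Step 1: in-window days for dose 3.** Earliest 25 + 25 = 50; latest 31 + 31 = 62. That is 62 - 50 + 1 = 13 possible days.

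**Step 2: visit exactly 7 days after dose 3.** It lies in days 62 to 64 only if dose 3 is on day 55, 56 or 57. It is outside for days 50 to 54 and 58 to 62, so 10 of 13.

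**Step 3: any visit 6 to 8 days after dose 3.** Overlap needs dose 3 + 8 >= 62 and dose 3 + 6 <= 64, so dose 3 on days 54 to 58. There is no overlap on days 50 to 53 and 59 to 62, so 8 of 13. The visits then fall on days 56 to 61 (early by the SAP) or 65 to 70 (late by the SAP).

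**Step 4: from days to patients.** Let S be the sum of the two interval errors, so dose 3 is on day 56 + S. No overlap means |S| >= 3. The documents give no distribution of dosing days, so three assumptions are shown, each with visit 4 always held at one week.

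| Assumed dose intervals | Calculation | Share with no overlap | Of 8 patients |
|---|---|---|---|
| Exactly 28 days | S = 0 | 0% | 0 |
| Normal error, SD 1 day, rounded to whole days, cut at +/- 3 | 2 x (0.0339 + 0.0066 + 0.0007 + 0.0000), for S = 3, 4, 5, 6 | 8% | 0.7 |
| Uniform over 25 to 31 days | 2 x (4 + 3 + 2 + 1) / 49 = 20/49 | 41% | 3.3 |

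In the SD 1 row the errors 0, 1, 2 and 3 days (either sign) have probabilities 0.383, 0.242, 0.061 and 0.006.

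**Step 5: alternative reading of the dose window.** If +/- 3 days is read as fixed around day 56 (days 53 to 59, 7 days), the exact one-week visit misses on 4 of 7 days (53, 54, 58, 59) and there is no overlap on 2 of 7 (53, 59). Both documents define the window between treatments, so the 13-day count is the one that follows the text.

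**Step 6: one 14-day deferral.** Dose 3 falls on about day 42 + 28 = 70, and the one-week window is days 76 to 78. The SAP window ends on day 64, before dose 3. Every visit 4 held after dose 3 is then scored as a deviation.

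**Step 7: after the fix.** If the SAP accepts either anchor, a visit 7 days after dose 3 is a deviation on 0 of 13 days.

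**The case against.** The strongest reply is that a site can nearly always satisfy both documents. The protocol offers week 9 as an equal option, and for every in-window dose 3 a visit on day 63 or 64 comes after the injection. The mismatch arises only when a site uses the one-week option and that date misses days 62 to 64. The protocol also asks for every effort to keep to 28 days, which makes the uniform assumption an upper illustration. This stands, and it is why the affected share may be close to zero. It does not remove the conflict: the one-week option is permitted, and after a 14-day deferral it is the only one of the two that falls after dose 3.

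A reader might infer more than the documents support.
- **That 8 or 10 of 13 is the proportion of patients affected.** It is not. Day 50 arises from one of the 49 interval pairs and day 56 from seven, so equal weighting of days overstates the extremes.
- **That visit 4 samples would be taken before dose 3.** Sites schedule from the protocol, whose one-week option covers a late dose 3. The SAP rule affects how the visit is scored.
- **That the main analyses are distorted.** The SAP's per-protocol set needs only the three injections. Its definition of a compliant patient rests on injection dates. Safety analyses include all enrolled patients.
- **That the exploratory grouping will certainly change.** SAP 4.2 refers this exploration to 5.1.2, where the contrast is treatment on or off schedule and is made only if required. Visits on days 56 to 61 are early, not delayed. The regrouping is possible, no more.

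**Conclusion.** The conflict is in the current text of both documents, and the SAP rule is wrong as written. Of the 13 in-window days for dose 3, an exact one-week visit breaches the SAP window on 10, and no visit within one week +/- 1 day can meet it on 8. The share of patients with no overlap runs from 0% to about 41% under the dosing assumptions shown, all of which suppose that visit 4 is held at one week. The consequence is limited to the visit 4 column of a descriptive adherence table and possibly one exploratory group.

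It might also be inferred that the protocol should be tightened to one week only, or that visit 5 should move. Neither follows. Forcing dose 3 + 7 +/- 1 would turn week 9 visits that are now permitted into deviations: with dose 3 on day 60, a visit on day 63 would fail. Visit 5 is week 14 +/- 1 week in both documents, so there is no conflict to resolve. The documents also give no ELISPOT kinetics from which to judge whether differing gaps since the last injection change the immune results.

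**What to change.** In SAP 4.2 and SAP Table 1, replace the single week 9 rule with the protocol's either-or wording for visit 4 (protocol 5.4 and Table 1), keeping +/- 1 day around each anchor. Do this before database lock. No change is needed to the protocol's visit 4 rule or to visit 5.

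Optionally, in SAP 5.1.2, list days since last injection (visit date minus date of last injection) beside each week 9 and week 14 immune result. With all doses in window, a visit on days 62 to 64 can be 62 - 62 = 0 to 64 - 50 = 14 days after dose 3, against 6 to 8 days on the one-week option. The listing would let readers see the gap.

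The cost is a few words in two places of the SAP, circulated to the DSMB for ratification under SAP 8. The optional listing is one derived variable from visit dates (Appendix 2, Table 4) and administration dates (Appendix 2, Table 5) already in the data files. No patients, visits or procedures are added.

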5.1. Analysis of outcomes

5.1.1. Primary outcome

Assessment of the safety of C19-A3 GNP administration in terms of adverse events at the dose used is the primary outcome. This includes general safety concerns, induction of hypersensitivity and exacerbation of β -cell specific autoimmunity with accelerated β -cell loss. All enrolled patients will be included in the following analysis.

General Safety

To address general safety concerns at screening and 0, 4, 8 and 14 weeks a physical examination will be conducted. A review of AEs will be performed at all visits according to seriousness, causality and expectedness. Types of AEs, body systems involved and outcomes of the AE will be categorised and analysed by incidence per person dose used. All AEs will be collated

Hypersensitivity

Patients will be observed for local and systemic reactions post injection. Number of local reactions will be analysed by incidence per person dose used, size of the erythema note and time taken for erythema note size to be reduced to < 1 cm will be analysed by mean and standard deviation. Systemic reactions will be analysed by incidence per person dose used. Therapies used and outcome will be counted and reported.

Exacerbation of β -cell specific autoimmunity with accelerated β -cell loss

Differences between week 0 and 14 will be calculated for each patient and summarised by mean and standard deviations for the following parameters:

- Measurement of islet cell autoantibodies (against insulin, GAD-65, IA-2 and ZnT8)
- Measurement of pro-inflammatory β -cell specific T cell responses (analytes to be defined)

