**Antigen delivery to be used in the current protocol.** In the current protocol, we will explore the safety of antigen specific immunotherapy using very small (< 5nm) gold nanoparticles coupled to a peptide of proinsulin C19-A3 which we have identified as being a naturally processed and presented T cell epitope of proinsulin that is frequently targeted in patients with type 1 diabetes who carry the susceptibility molecule, HLADRB1\*0401 (~35% of the patient population)(24, 78). We have completed a phase 1A study of intradermal delivery of this peptide (alone) in patients with type 1 diabetes (24) up to doses of 100ug and no evidence of toxicity was observed (79). At the lower dose tested (10mcg) potentially protective IL-10 responses to the peptide were induced in 5/18 subjects (79). We have also recently completed a phase 1b study of this peptide in new-onset type 1 diabetes patients giving more doses (12 versus 3), more frequently (every 14 days rather than monthly) with no evidence of toxicity other than transient local red reactions seen previously. The small size and high solubility of this peptide allows it to be easily coupled to small nanoparticles. In addition, it does not have the bioactivity of insulin and hence is free from the risk of hypoglycaemia associated with the intact molecule. In a future study, we plan to study the additional effect of linking delivery of these particles to IL-10 to reduce inflammation and promote the generation of regulatory T cells. We have termed the overall approach, “Enhanced Epidermal – Antigen Specific Immunotherapy” (EE-ASI).

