### **Conditions for interruption of dosing to individuals.**

If there is evidence of hypersensitivity (i.e. wheal as well as flare), subjects can have paracetamol and antihistamines and continue in the trial as per the study schedule.

Injections and treatment will be immediately discontinued (but follow up will continue) in any subject who:

1. Experiences a worsening local wheal or flare reaction at the injection site exceeding 5 cm.
2. Experiences a serious adverse reaction or an allergic event suggestive of systemic hypersensitivity requiring more than local therapy (e.g. requiring steroids, bronchodilators, or adrenaline).
3. Becomes pregnant (see section 8 withdrawal/exit criteria).

**Conditions for suspending further dosing to all subjects.** If any individual in the study experiences a SUSAR further dosing of all subjects at all sites will be suspended pending review by the Data Safety Monitoring Board and discussion with the CI and Sponsor. Advice will be sought from the DSMB regarding re-starting the study.

A substantial amendment application will be submitted to the Regulatory Agencies to resume the trial.

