## 10.2 Hypersensitivity

Induction of hypersensitivity to C19-A3 GNP will be assessed by a period of observation of subjects and during the immediate period after peptide injection. Local hypersensitivity may manifest as an increasing wheal and flare reaction at the site of peptide injection. The first patient dosed with GNP-peptide will be observed for 6 hours post dose – see section 7.3. Any adverse reactions will be communicated to the other trial treatment site by email, in addition to the standard pharmacovigilance procedures. Subsequent subjects will also be observed for 6 hours. If no serious adverse events are observed post first dose, subsequent visits will have an observation period of a minimum of 1 hour post dose, or 2 hours if there are any symptoms of signs of hypersensitivity. This time period has been chosen as the only anticipated severe reactions is one of hypersensitivity which, if systemic, would be apparent within 60 mins of intradermal dosing.

Observation will be by inspection of the injection site at 5 minute intervals for the first 15 minutes and then 15 minute intervals for a further 45 minutes. If any reaction is present and not resolving over this period, observation will be extended to 15 minute intervals until the reaction is reducing and < 1cm in diameter. Maximum size of any redness or swelling at the injection site will be recorded at each visit at which study drug is given (visits 1-3). Systemic hypersensitivity may manifest as shortness of breath; skin rash; tissue swelling; collapse. Subjects will be inspected for such signs at 5-minute intervals for the first 15 minutes and then at 15 minute intervals for a further 45 minutes. Pulse and blood pressure will be recorded at 15 minute intervals over this time. Any adverse events during this observation period will be recorded. To minimise any risk that might result from hypersensitivity:

- IMP administration should ONLY performed in a clinical research environment appropriate for phase 1 studies in which resuscitation facilities are immediately available.
- Facilities for treatment of a major hypersensitivity reaction, adrenaline, oxygen, intravenous infusion, head-down position, blood pressure and pulse monitoring should be available in the immediate environment of the subject, with access to hydrocortisone and antihistamines.
- Subjects should not be treated by a lone-worker unless he/she has immediate access to clinically trained support.

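### SAP 5.1.1 reports local hypersensitivity as one undifferentiated count and sizes only erythema, so it omits swelling and cannot separate anticipated redness from wheal with flare

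*SAP*

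**What the plan says.** Induction of hypersensitivity is named in the primary objective (protocol 4.1, SAP 1.2), and SAP 5.1.1 places it inside the primary outcome. The local analysis there has two parts. The first is "Number of local reactions will be analysed by incidence per person dose used, size of the erythema note". The second is "time taken for erythema note size to be reduced to < 1 cm will be analysed by mean and standard deviation". The same paragraph adds "Systemic reactions will be analysed by incidence per person dose used" and "Therapies used and outcome will be counted and reported".

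The protocol describes the sign in several ways:

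- Section 7, conditions for interrupting dosing in individuals, opens with "If there is evidence of hypersensitivity (i.e. wheal as well as flare", closing the parenthesis there.
- Section 10.2 states "Local hypersensitivity may manifest as an increasing wheal and flare reaction at the site of peptide injection".
- The recording rule in 10.2 is "Maximum size of any redness or swelling at the injection site will be recorded at each visit", for the three dosing visits. Extended observation in 10.2 runs until the reaction, not specifically the redness, is shrinking and under 1 cm.
- The individual discontinuation criterion in section 7, repeated in SAP 2.2.2, is a worsening wheal or flare reaction larger than 5 cm.

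Redness is anticipated. Protocol 3.2 reports, for an earlier study of the peptide alone, "no evidence of toxicity other than transient local red reactions seen previously". Section 6.14 says that some people may have a painless red area lasting three months or longer.

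**The concern.** The SAP's analysis text is narrower than the protocol's description and measurement of the reaction. Swelling is recorded under 10.2 but has no planned summary. The 1 cm time is defined for erythema, whereas 10.2 defines it for the reaction. The count does not say which sign makes a local reaction qualify.

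This is a first-in-human study, and protocol sections 7 and 10.2 name hypersensitivity as the only severe reaction anticipated. Readers planning later trials will want to know how many injections were followed by wheal with flare, how many by redness alone, and whether the pattern changed from dose 1 to dose 3. The summary as written answers none of these directly. The 5 cm criterion also has no tally in the analysis text.

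**Working it through.** The documents give no event rate, precision target or power for this outcome. SAP section 4 says the analysis is descriptive, and N = 8 comes without a formula. There is no plan figure to reproduce, so the check is mainly a comparison of texts.

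**Texts side by side**

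| Item | Protocol | SAP 5.1.1 |
|---|---|---|
| Sign of local hypersensitivity | Wheal with flare (7; 10.2, as a possible manifestation) | Local reaction, sign not stated |
| Size | Redness or swelling, maximum (10.2) | Erythema only |
| Time to under 1 cm | The reaction (10.2) | Erythema only |
| Worsening wheal or flare above 5 cm | Discontinuation criterion (7; also SAP 2.2.2) | No count |

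**Do the SAP data files fill the gap?** Table 5 at the end of the SAP has a single yes/no field for skin reaction. Its footnote sends the details to a separate listing from the post-injection skin reaction log, by patient and visit. The fields of that log are not named. A listing by sign may therefore be possible, but no summary by sign is planned.

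**How far apart can the two counts be?**

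Inputs: 8 subjects (protocol 14) and 3 doses each (protocol 5.2). Person-doses = 8 x 3 = 24 if exactly 8 subjects receive all doses; replacement subjects would raise this. The reaction frequencies below are assumptions.

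| Injections with any local reaction (assumed) | SAP incidence | Possible wheal-with-flare count | Possible wheal-with-flare incidence |
|---|---|---|---|
| 6 | 6/24 = 25% | 0 to 6 | 0 to 25% |
| 12 | 12/24 = 50% | 0 to 12 | 0 to 50% |
| 24 | 24/24 = 100% | 0 to 24 | 0 to 100% |

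In every row the reported incidence is compatible with no wheal-with-flare reaction at all and with every reaction being one.

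Precision if none were seen: the exact two-sided 95% upper limit for 0 out of n is 1 - 0.025^(1/n).

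- n = 24 injections: 1 - 0.025^(1/24) = 14.2%. This treats doses as independent, which repeated doses in one subject are not.
- n = 8 subjects: 1 - 0.025^(1/8) = 36.9%.

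Even a clean result by sign would be imprecise. It could still be stated, whereas the summary as planned cannot state it.

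**The case against.** A reader might infer that the SAP measures the wrong clinical sign, or that wheal goes uncounted. The documents do not support either. Flare is one of the two signs in the section 7 gloss, and redness is among the things 10.2 tells sites to measure. The discontinuation criterion is met by wheal or flare, so erythema size does bear on it. A wheal is a local reaction and falls within the count; it is just not separated.

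A reader might also infer that redness should leave the hypersensitivity outcome and be reported as tolerability. That is not supported either. The gloss in section 7 is a parenthesis, and 10.2 says only that local hypersensitivity may take the wheal-and-flare form. Sections 6.15 and 10.2 also treat delayed Type 4 reactions as hypersensitivity, and a footnote to protocol Table 1 ties the optional skin tests to persistent reactions. The documents call the anticipated redness neither flat nor non-specific.

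The case against has further force on three points:

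- With about 24 injections, the listing by patient and visit could show individual reactions and any growth over doses, if the log records the signs. It cannot be said that such a pattern would be hidden.
- The 5 cm criterion leaves a partial trace: Table 8 codes study drug action for each adverse event, and Table 5 records delayed or missed injections with a reason.
- Systemic reactions, therapies, outcomes and all adverse events are analysed separately, so most of the primary outcome is untouched.

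These points limit the scope of the concern. They do not supply the missing summary of swelling or the missing separation by sign.

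**Conclusion.** The concern holds in a limited form. As written, the local hypersensitivity summary in SAP 5.1.1 omits swelling and cannot distinguish anticipated redness from wheal with flare. For any assumed local reaction rate from 25% to 100% of 24 injections, the wheal-with-flare rate could lie anywhere from zero to that same value. This ambiguity follows from the wording and does not depend on the assumed rates.

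The defect is one of incompleteness in the local part of one component. It does not invalidate the primary safety outcome. The conclusion assumes that the analysis text is followed as it stands. Whether the skin reaction log already separates the signs cannot be determined from the documents; if it does, only the SAP needs to change.

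**What to change.** In SAP 5.1.1:

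1. Keep the overall local reaction count per person-dose.
2. Also classify each injection as no reaction, redness only, wheal only, or wheal with flare, and tabulate by subject and dose number. Keep redness-only reactions within the hypersensitivity tables.
3. Summarise swelling size and its time to resolution beside the erythema summaries.
4. Count injections meeting the 5 cm criterion as already stated in protocol section 7 and SAP 2.2.2.

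Confirm that the post-injection skin reaction log records wheal and flare diameters separately, and add a field if it does not. Reconcile the differing wording in protocol sections 7 and 10.2 and SAP 2.2.2 and 5.1.1. This is a matter of consistent terms and implies no change to any clinical rule.

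The cost is slightly more tabulation and possibly one extra log field. The injection-site inspections are already scheduled in protocol 10.2, so no visit or procedure is added. The SAP change would go to the monitoring board under SAP section 8.
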